## SCHEMA

### OBJECTIVES

There are two primary objectives of this study. The first is to compare 10-week changes in Insomnia Severity Index (ISI) scores in HIV-infected adults with clinically relevant insomnia severity and who are already receiving virologically suppressive antiretroviral therapy (ART) and are then randomized to either treatment with the SHUTi cognitive behavioral therapy program or to Usual Care (UC). The second is to compare measures of frailty and cognitive function between HIV-infected, virologically suppressed adults with and without clinically relevant insomnia severity.

### DESIGN

Our objectives will be met by performing two studies. The first is a 10-week, randomized, controlled, single-blinded, two-arm, parallel group, pilot trial at a single center and the second is a cross-sectional two-group comparative study.

Study I: A total of 40 persons with HIV may be screened and consented to identify the 32 participants to be enrolled and randomized into the pilot trial. We expect a screen failure rate of 20%. These participants will be  $\geq 18$  years old, have been receiving antiretroviral therapy with an HIV viral load  $< 75$  copies/mL within three months of the Entry Visit, and have an ISI score  $\geq 11$  within three months of the Entry Visit. These participants will be randomized 1:1 (stratified by age  $<40$  vs.  $\geq 40$  years) to either insomnia treatment with the SHUTi cognitive behavioral therapy program (N=16) or usual care (N=16).

Study II: The 32 participants with insomnia from Study I will then be compared to a similar group of 12 HIV-infected patients but with an ISI score  $< 11$  within three months of the Entry Visit. Six will be  $<40$  years old and the other six will be  $\geq 40$  years old). Approximately 15 persons with HIV may be screened and consented to identify this second group of 12 participants without insomnia. We expect a screen failure rate of 20%.

### DURATION

Each individual participant in Study I will be followed for approximately 10 weeks. Those enrolled specifically into Study II will have a single one-day study visit.

### POPULATION

All participants will be HIV-infected, 18 years of age or older, will have received stable ART for at least 3 months, will have a HIV viral load of less than 75 as per a measurement that was obtained as a part of standard clinical care, and have this load measured within 90 days of study entry. Participants will be recruited from the infectious diseases outpatient clinics of Eskenazi Health Hospital and the Indiana University Health Hospitals.

## 1.0 STUDY OBJECTIVES

### 1.1 Study I Primary Objective

1.1.1 To compare 10-week changes in ISI scores between those undergoing insomnia treatment using the SHUTi cognitive behavioral therapy program vs those receiving Usual Care (UC).

### 1.2 Study I Secondary Objectives

1.2.1 To compare 10-week changes in Pittsburgh Sleep Quality Index (PSQI) scores and brief sleep diaries between those undergoing insomnia treatment using the SHUTi cognitive behavioral therapy program vs those receiving Usual Care (UC).

1.2.2 To compare 10-week changes in PHQ-9, SF-36, and WHOQOL-HIV Brief scores between those undergoing insomnia treatment using the SHUTi cognitive behavioral therapy program vs those receiving Usual Care (UC).

### 1.3 Study II Primary Objectives

1.3.1 To compare FRAIL scale, Fried Index, and SPPB scores between those with ISI scores  $\geq 11$  and those with ISI  $< 11$ .

1.3.2 To compare CSRQ-25 and Digit Symbol Substitution Test (DSST) scores between those with ISI scores  $\geq 11$  and those with ISI  $< 11$ .

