### 1.4 Study II Secondary Objectives

1.4.1 To correlate ISI scores with each of the following: PSQI, PHQ-9, SF-36, WHOQOL-HIV Brief, FRAIL scale, Fried Index, SPPB, CSRQ-25, and DSST.

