### 3.0 STUDY DESIGN

#### 3.1 Overview

Our objectives will be met by performing two studies. The first is a 10-week, randomized, controlled, single-blinded, two-arm, parallel group, pilot trial at a single center and the second is a cross-sectional two-group comparative study.

Study I: A total of 40 persons with HIV may be screened and consented to identify the 32 participants to be enrolled and randomized into the pilot trial. These participants will be  $\geq 18$  years old, have been receiving antiretroviral therapy for at least three months with an HIV viral load  $< 75$  copies/mL, and have an ISI score  $\geq 11$ . These participants will be randomized 1:1 (stratified by age  $<40$  vs.  $\geq 40$  years) to either insomnia treatment with the SHUTi cognitive behavioral therapy program (N=16) or usual care (N=16).

Study II: The 32 participants with insomnia from Study 1 will then be compared to a similar group of 12 HIV-infected patients but with an ISI score  $< 11$ . Six will be  $<40$  years old and the other six will be  $\geq 40$  years old). Approximately 15 persons with HIV may be screened to identify this second group of 12 participants without insomnia.

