#### 6.2.5.10 Fried Index

The Fried Index is a measure of frailty (33). It is composed of 5 criteria:

- Self-reported unintentional weight loss of  $\geq 10$  pounds or 5% in the prior year (should be verified with medical records if possible)
- Reduced grip strength (<23 lbs. for women, <32 lbs. for men as measured in the dominant hand using a dynamometer; this is averaged over 3 assessments)
- Self-reported exhaustion (person states they are exhausted 3 or more days per week; exhaustion is feeling “everything I do is an effort” or “sometimes I just cannot get going”)
- Reduced gait speed (>0.8 m/sec over 4 meters; this is averaged over 2 assessments)
- Self-reported low physical activity (being “limited a lot” in vigorous activities from the SF-36 form)

One point is given to each positive criterion with zero points indicating no frailty, 1-2 points indicating pre-frailty, and 3-5 points indicating frailty.

The Fried Index will be assessed only at the Entry Visit.

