#### 6.2.5.11 Short Physical Performance Battery (SPPB)

The SPPB assesses physical functioning and includes standing balance (3 stances), walking speed, and sit-to-stand test time. Each task is rated from zero (indicating inability to complete the task) to four points (indicating best performance) based on established criteria (33), and results from the 3 tasks are summed. Standing balance is measured by a hierarchical performance scale based on side-by-side stance, “semi-tandem” stance (heel to 1st MTP joint), and full tandem (heel to toe), with each stance being held up to for ten seconds. Walking speed is measured in m/sec based on the faster of two 4-m walks at usual pace. Sit-to-stand test time is assessed by the time required to perform five uninterrupted repetitions of sit-to-stand using a firm chair and without use of the arms. An SPPB score of less than 9 is highly predictive for subsequent disability and is considered low function, 9–11 points moderate function, and 12 points (no deficits) high function. A standardized scoring sheet (see Appendices) will be used for this assessment.

The SPPB will only be assessed at the Entry Visit.

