## 9.0 STATISTICAL CONSIDERATIONS AND DATA MANAGEMENT

### 9.1 General Considerations

Data management and statistical analyses will be the responsibility of the study team. The randomization sequence, though, will be generated by a member of the Department of Biostatistics. Parameter estimates and relevant summary statistics will be reported for both efficacy and side effects. Continuous variables will be summarized by means, medians, minima, maxima, and standard deviations. Categorical variables will be summarized by frequencies and percentages. Additional exploratory analyses will be performed when appropriate. Normality of variables will be checked and, if violated, nonparametric methods will be adopted. Changes from the analysis plan will not require an amendment to the protocol unless it changes a significant feature of the study.

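### Study II analyses physical performance only through scored totals. An SPPB ceiling is likely though not certain, so raw gait speed and sit-to-stand time should be pre-specified alongside the scores.

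*Combined protocol and SAP*

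**What the plan says.** Section 1.3.1 gives the first Study II primary objective: "To compare FRAIL scale, Fried Index, and SPPB scores between those with ISI scores" of at least 11 and those below 11. Section 1.4.1 follows the same pattern ("To correlate ISI scores with each of the following: PSQI, PHQ-9, SF-36", then the remaining scales), and hypothesis 2.1.2 is also framed in scores. No raw performance measure is named as an outcome.

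The raw measures are nevertheless taken. For the SPPB (section 6.2.5.11), "Walking speed is measured in m/sec based on the faster of two 4-m walks at usual pace", and five sit-to-stand repetitions are timed. The best total is defined as "12 points (no deficits) high function". For the Fried Index (section 6.2.5.10), gait speed is averaged over two assessments and grip over three, each is reduced to a yes/no item, and "One point is given to each positive criterion with zero points indicating no frailty".

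Section 3.1 says that the 32 Study I participants "will then be compared to a similar group of 12 HIV-infected patients but with an ISI score" below 11, six of them under 40 and six aged 40 or over.

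Section 9 contains no analysis written for Study II: 9.10 concerns Week 10 ISI, and 9.11 compares Usual Care with SHUTi. What applies is the general rule in 9.1, "Normality of variables will be checked and, if violated, nonparametric methods will be adopted", and a general allowance there for exploratory analyses.

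**The concern.** A total with a fixed best value cannot separate people who are all at that value. Several features of the sample point towards good performance. Entry is from age 18, half of the small control group is under 40, and sections 4.2.4, 4.2.5 and 4.2.13 exclude vascular disease, heart failure, and musculoskeletal or neurologic disorders that get in the way of the procedures. If most controls score 12 on the SPPB, the total will fail the normality check and go to a rank test with heavy ties. The correlations with ISI in 1.4.1 would be weakened in the same way.

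What is at stake is the usefulness of the estimate. Section 2.3 describes frailty as a new area for the group and wants these data to support later trials. A mean difference in m/sec or seconds with a confidence interval can be used to plan such a trial, whereas a heavily tied rank comparison gives little for that purpose.

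**Working it through.** **Inputs from the documents.** Group sizes are 32 and 12 (section 3.1). A two-sided 5% level is written for the Study I primary analysis (section 9.10) and is assumed here for Study II. The SPPB is the sum of three tasks scored 0 to 4 (section 6.2.5.11).

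**The plan's own figures.** Section 9.2 and the Schema give only recruitment arithmetic, which reproduces: 12/(1 − 0.25) = 16 per arm, 32/(1 − 0.20) = 40 screened, 12/(1 − 0.20) = 15 screened. No power, SD, effect size or share at the SPPB maximum is stated for Study II, so the ceiling shares and effect sizes below are assumptions.

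**1. What an uncapped measure can do at this size.**
- Standard error in SD units: √(1/12 + 1/32) = 0.3385.
- Difference detectable with 80% power: (1.960 + 0.842) × 0.3385 = 0.95 SD. For 90% power: (1.960 + 1.282) × 0.3385 = 1.10 SD.
- 95% CI half-width: 1.96 × 0.3385 = 0.66 SD, or 0.68 SD with the t quantile on 42 degrees of freedom.

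**2. One measure against a capped version of itself.** Simulation with normal latent performance, a score in 0.5 SD steps below the cap, and the Mann-Whitney test on both (3,000 runs per cell):

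| True difference | Raw | 50% of controls at best | 70% | 80% | 90% |
|---|---|---|---|---|---|
| 0.5 SD | 29% | 25% | 20% | 15% | 7% |
| 0.8 SD | 60% | 56% | 48% | 39% | 27% |
| 1.0 SD | 80% | 77% | 71% | 63% | 46% |

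This isolates the cost of capping. It is not the choice that the plan faces, because the SPPB sums three tasks and a raw gait speed is only one of them.

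**3. One raw task against the summed three-task score.** Assumptions: 0.8 SD difference on each task, inter-task correlation 0.5, equal cut-offs, 32 against 12, with a t-test on the raw task and a Mann-Whitney test on the sum.

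| Controls at maximum total | One raw task | Summed score | Raw minus score |
|---|---|---|---|
| 50% | 63% | 72% | −9 points |
| 65% | 63% | 64% | −1 point |
| 80% | 63% | 52% | +11 points |
| 90% | 63% | 35% | +28 points |

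A repeat run with each task scored 0 to 4 in 0.5 SD steps agreed to within 2 points. Another set of runs with a weaker effect per task (about 37% power for one raw task) gave 40, 36, 25 and 15% for the sum, which is the same pattern. Summing three tasks offsets a moderate ceiling, and the raw measure gains only when the ceiling is heavy.

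**4. Whether the argument reaches the Fried total.** Three of its five items are self-reported (weight loss, exhaustion, low activity), and exhaustion is plausible in people selected for insomnia. The gait item is labelled as reduced speed but printed as greater than 0.8 m/sec. Taken as printed, the share scoring a point is 1 − Φ((0.8 − mean)/SD). With assumed means of 1.0 to 1.3 m/sec and SDs of 0.15 to 0.25, this runs from 1 − Φ(−0.8) = 79% (mean 1.0, SD 0.25) to about 100% (mean 1.3, SD 0.15). Totals would then collect at 1 or more, not at the best value of 0.

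**The case against.** The strongest case against is that the SPPB ceiling is a guess. The documents state no distribution, and the under-40 quota binds only six controls. The 32 participants with insomnia are stratified by age without a quota. Exclusion 4.2.13 removes people who have difficulty doing the procedures, not slow performers, and section 2.2 cites more frailty in HIV. This stands: a ceiling is likely and no more than that, and at 50 to 65% of controls at maximum the summed score is as good as one raw task or better.

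Second, Study II asks about frailty, and the three instruments carry interpretable categories. A reader might infer that they should give way to raw measures. The documents do not support that. It would rewrite a primary objective, and FRAIL has no timed component to substitute.

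Third, section 9.2 says that significant differences are not expected. A reader might infer that capping is what would turn a real effect into a null result. Step 1 shows otherwise: an uncapped measure also needs about 0.95 SD for 80% power. The gain lies in the estimate.

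Fourth, section 9.1 allows further exploratory analyses, so raw measures are not ruled out. But it names none, and choosing one after seeing the scores would be post hoc. That leaves the case for naming them now.

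**Conclusion.** The point holds as a modest, worthwhile addition. Sections 1.3.1 and 1.4.1 analyse physical performance only through totals although finer measurements are taken, and the age range and exclusions make an SPPB ceiling plausible. Under the assumptions of step 3, one raw task gains about 11 points of power at 80% of controls at maximum and 28 points at 90%. At 65% there is no gain, and at 50% the score is ahead by 9 points. These sizes depend on assumed ceiling shares, effect size, inter-task correlation and cut-offs, none of which the documents give.

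A reader might also infer that Fried totals will bunch at zero. The text does not support this: the self-report items can spread the total, and the gait criterion as printed would move most people off zero. That criterion contradicts its own label and has to be reconciled before the Fried total can be interpreted either way.

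**What to change.** - Keep FRAIL, Fried and SPPB as the stated endpoints.
- Pre-specify raw 4-m gait speed (m/sec) and five-repetition sit-to-stand time (seconds), and optionally grip adjusted for sex, as accompanying continuous outcomes for 1.3.1 and 1.4.1. State which gait value is used, since section 6.2.5.11 takes the faster of two walks and section 6.2.5.10 the average.
- Report mean differences with 95% CIs among those who complete the task, and separately a rank-based analysis that gives non-performers the worst rank. The two must be kept apart, because a mean difference cannot be computed from an assigned rank.
- Label these comparisons as estimation.
- Confirm that the raw values are entered in the database. Section 6.2.5.11 refers to a scoring sheet but does not say that the times themselves are stored.
- Reconcile the label and the inequality of the Fried gait item.

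The cost is analysis wording, two or three more outcomes to tabulate, more comparisons to label, and possibly a few database fields. No new visit or test is needed.

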### 1.4 Study II Secondary Objectives

1.4.1 To correlate ISI scores with each of the following: PSQI, PHQ-9, SF-36, WHOQOL-HIV Brief, FRAIL scale, Fried Index, SPPB, CSRQ-25, and DSST.

## 2.0 HYPOTHESES, BACKGROUND, AND INTRODUCTION

### 2.1 Hypotheses

2.1.1 Treatment with SHUTi will reduce ISI, PSQI, PHQ-9, SF-36, and WHOQOL-HIV Brief scores at 10 weeks when compared to UC.

2.1.2 HIV-infected patients with ISI scores  $\geq 11$  will have higher FRAIL scale, Fried Index, and SPPB scores and lower CSRQ-25 and DSST scores compared to those with ISI scores  $< 11$ .

### 2.2 Background

*Insufficient sleep* is a highly prevalent and harmful health behavior that contributes to poor mental and physical health outcomes (1). Here, insufficient sleep is defined as the presence of insomnia – frequent and persistent difficulty in initiating or maintaining sleep causing functional impairment or distress (2-4). A 2006 Institute of Medicine report (5) stated that "the cumulative effects of sleep loss and sleep disorders represent an under-recognized public health problem and have been associated with a wide range of health consequences."

Therefore, promoting *sufficient sleep*, a positive health behavior, may alter the adverse mental and physical health aging trajectories of vulnerable adults.

In the general population, insomnia has been linked to a higher risk for the development of several comorbid conditions, including cardiovascular disease (CVD) (6), frailty (7), cognitive impairment (8, 9), and depression (10). Plausible underlying mechanisms for the relationship between insomnia and cardiovascular disease include biological factors (systemic inflammation, altered coagulation, autonomic dysfunction), behavioral factors (smoking, excessive alcohol use, physical inactivity), and traditional CVD risk factors (obesity, diabetes, hypertension) (11). Insomnia may lead to frailty through its potential to lead to cardiovascular and cerebrovascular disease, impaired physical functioning, and reduced daytime physical and social stimulation (7). Insomnia may impair cognitive function by preventing normative CNS repair functions that occur during nocturnal sleep or by reducing daytime intellectually stimulating activities (9).

While it is not uncommon for insomnia to be conceptualized as a depressive symptom in clinical settings, current diagnostic manuals (e.g., DSM-5) assert that insomnia is not simply a symptom of other conditions and exists as a clinical problem warranting attention as an independent diagnosis – regardless of medical and psychiatric co-morbidities, including depression (12, 13). Moreover, research examining the directionality between insomnia and depression consistently finds that, insomnia increases the risk of future depression (14, 15) and less consistently finds that depression increases the risk of future insomnia (16-20). This suggests that insomnia manifests independently of depression and likely precedes, rather than follows, depression onset.

HIV infection is itself associated with an increased prevalence of insomnia (21), as well as increased risks for cardiovascular disease (22), frailty (21, 23), cognitive impairment (24), and depression (25). Thus, it is possible that the detrimental effects of insomnia on these comorbid complications may be particularly problematic in those with HIV. However, it is not known if treating insomnia would reduce the risk of developing these comorbid conditions in the HIV-infected population.

The American College of Physicians has stated that the preferred treatment for chronic insomnia in adults is not pharmacologic therapy but rather cognitive behavioral therapy for insomnia (CBT-I) due to its more significant results in terms of both efficacy and longevity of response (26). In addition, CBT-I is not associated with adverse effects that may complicate therapy with sleep medications (e.g. abuse potential, cognitive impairment, drug interactions with HIV antiretrovirals, accidents). However, providing CBT-I has proven difficult in environments where there are insufficiently trained providers. In addition, patients may not be able to attend dedicated sessions with a CBT-I therapist due to financial or time restraints. To address these issues, an evidence-based, cognitive-behavioral, online intervention for insomnia called Sleep Healthy Using The Internet (SHUTi) was developed by our colleague and consultant, [name]. SHUTi is based on a well-established face-to-face CBT-I (27, 28) and incorporates sleep restriction, stimulus control, sleep hygiene, cognitive restructuring, and relapse prevention. A comparison of CBT-I to insomnia medications revealed that patients receiving CBT-I have similar short-term and better long-term outcomes (29). There is also a preference for and greater acceptance of CBT-I (30). Each SHUTi session has the same structure: the main content, a homework screen with options, and a summary of the main points. The Internet requirements are minimal (SHUTi can run on a dial-up connection). Although SHUTi has proven quite successful in treating insomnia in the general population, *this intervention has not been tested specifically in an HIV-infected population for whom there are unique characteristics and stressors that may influence the response to this intervention*. For example, the previous studies using SHUTi involved primarily white, educationally-advantaged persons as opposed to our local HIV patient population that is majority black and from lower socioeconomic status (SES) backgrounds with a chronic, stigmatizing disease.

## 2.3 Study Rationale

Our long-term goal is to use SHUTi as an intervention to treat insomnia in patients with HIV infection in order to improve long-term outcomes (including reducing the risk of cardiovascular disease, frailty, cognitive

functioning, and depression) and quality of life. Our group has extensive experience in cardiovascular disease prevention research (e.g. our currently NIH-funded R01 trial of internet-based CBT depression therapy in HIV to reduce inflammation and improve endothelial function), but we also want to develop research expertise in HIV-related frailty and cognitive impairment, as these are increasingly important outcomes (and areas of interest to the NIH) in the aging HIV population.

There are several R01-level NIH funding mechanisms focused on cardiovascular disease, frailty, cognitive impairment, and depression in HIV (PA-16-427, PAR-17-321). We believe that treating insomnia in HIV is a unique method by which to improve all of these endpoints. But to be competitive for these funding opportunities, we will first need to develop preliminary data showing that SHUTi can be effective both in our hands and in our target population. Of note, we already have preliminary cross-sectional data demonstrating an inverse relationship between more severe insomnia symptoms using the PSQI scale and lower endothelial function (as measured by flow-mediated dilation of the brachial artery in [name] CTSI Vascular Imaging Core) in HIV-infected patients on virologically-suppressive antiretroviral therapy (ART). *However, we need to develop additional preliminary data in a similar group of HIV-infected patients that relate insomnia measures to frailty and cognitive impairment, as these are new areas of research for our group.* If we can demonstrate that insomnia is negatively related to frailty and cognitive impairment in HIV and that SHUTi improves sleep outcomes in this population, then we can more readily justify randomized trials of SHUTi to improve these measures in HIV and thus be more competitive for extramural funding.

